7.2.1 Relationship of Adverse Event to Study Drug

The following adverse event attributes must be assigned by the investigator: adverse event diagnosis or syndrome(s) (if known, signs or symptoms if not known); event description (with detail appropriate to the event); dates of onset and resolution; severity; assessment of relatedness to study drug and action taken. The investigator may be asked to provide follow-up information, discharge summaries, and extracts from medical records or eCRFs.

If applicable, the relationship of the adverse event to the study drug will be assessed by means of the question: “Is there a reasonable possibility that the event may have been caused by the study drug?” The investigator should respond to this question with either Yes or No.

7.2.2 Adverse Event Severity

The severity of adverse events should be graded as follows:

- Mild – Usually transient in nature and generally not interfering with normal activities
- Moderate – Sufficiently discomforting to interfere with normal activities
- Severe – Prevents normal activities

Medically significant adverse events considered related to the study drug by the investigator or Sponsor will be followed until resolved or considered stable.

It will be left to the investigator’s clinical judgment to determine whether an adverse event is related and of sufficient severity to require the subject’s removal from treatment or from the study. A subject may also voluntarily withdraw from treatment due to what he or she perceives as an intolerable adverse event. If either of these situations arises, the subject should be strongly encouraged to undergo an end-of-study assessment and be under medical supervision until symptoms cease or the condition becomes stable.

7.3 Serious Adverse Event Reporting Procedures

Serious Adverse Events, including laboratory test abnormalities fulfilling the definition of serious, after the first dose, and during follow-up period must immediately (within 24 hours of the investigator’s awareness) be reported to the person/parties as detailed in the study file. A Serious Adverse Event form must also be completed within 1 day of the investigator’s awareness and forwarded to the designated person/parties as detailed in the study file. Each Serious Adverse Event must be followed up until resolution or stabilization by submission of updated reports to the designated person/parties.

Reporting of SAEs begins from the first administration of the study drug through within 30 days after the last dose of study drug. Events assessed by the Investigator as related to study drug (or

having an unknown relationship at the time of reporting) should be reported within 24 hours regardless of the number of days since the last dose.

For all deaths, available autopsy reports and relevant medical reports should be faxed to Sponsor or their designee. For this reporting process, subject assessments must be made 30 days after administration of the last dose of study drug. Deaths assessed by the Investigator as related to study drug (or having an unknown relationship at the time of reporting) should be reported within 24 hours regardless of the number of days since the last dose.

If a subject is permanently withdrawn from the study because of a serious adverse event, this information must be included in the initial or follow-up Serious Adverse Event Report Form as well as the End of Study Case Report Form.

When required, and according to local law and regulations, serious adverse events must be reported to the institutional review board and Regulatory Authorities.

7.4 Procedures for Managing Microhemorrhages and Cerebral Vasogenic Edema

MRI scan will be performed at screening, Visit 9 (Week 12), Visit 13 (Week 30), Visit 14 (Week 52), and/or Early Termination Visit. The protocols for MRI scans should include fluid-attenuation inversion recovery (FLAIR) and T2-weighted gradient-recalled-echo (GRE) sequences. Standards for the detection of cerebral microhemorrhage or superficial siderosis will include: 2D T2 GRE; field strength of 1.5 Tesla or greater; slice thickness of 5mm or less; Echo Time (TE) of 20 ms or greater. Standard FLAIR sequences are generally appropriate for the detection of cerebral vasogenic edema.

Subjects who are found to have new clinically asymptomatic microhemorrhages will be followed up closely, and a follow-up MRI will be done to evaluate the stability of those lesions.

All Principal Investigators will be notified of the possible occurrence of cerebral vasogenic edema, its imaging manifestations, and the clinical signs and symptoms that may accompany this phenomenon. They will also be told of the measures to be taken if cerebral vasogenic edema occurs. Those measures will include more frequent serial MRI scans until the imaging abnormalities resolve, and consideration of treatment with high-dose dexamethasone if symptoms are severe.

8. USE OF DATA AND PUBLICATION

All data and results and all intellectual property rights in the data and results derived from the study will be the property of the sponsor, who may utilize the data in various ways, such as for submission to government regulatory authorities or disclosure to other investigators. The investigator, while free to utilize data derived from the study for scientific purposes, must discuss any publication with the sponsor prior to release and obtain written consent of the sponsor on the intended publication. The sponsor recognizes the right of the investigator to publish the results upon completion of the study. However, the investigator must send a draft manuscript of the publication or abstract to the sponsor thirty days in advance of submission in order to obtain approval prior to submission of the final version for publication. This will be reviewed promptly and approval will not be withheld unreasonably. In case of a difference of opinion between the sponsor and the investigator(s), the contents of the publication will be discussed in order to find a solution that satisfies both parties.

The investigator is encouraged to participate in the evaluation of the data for scientific purposes but is expected to work with the sponsor in the development of any scientific presentation or publication. Since the sponsor authors will be included, it is expected that all co-authors of the manuscripts will have an opportunity for feedback in the content and conclusions. The technical and editorial resources of the sponsor will be available to assist in the development of abstracts, presentations, and publications regarding this study and it is expected that drafts will be sent to the sponsor with adequate time for input and revisions prior to submission.

10. APPENDICES

Appendix 1. Laboratory Parameters

Appendix 2. ADAS-Cog (Alzheimer's Disease Assessment Scale-cognitive subscale)

Appendix 3. MMSE (Mini-mental status examination)

Appendix 4. CDR-SOB (Clinical Dementia Rating-Sum of Box)

Appendix 5. NPI (Neuropsychiatric Inventory)

Appendix 6. GDS (Geriatric Depression Scale)

Appendix 7. ADCS-ADL (Alzheimer's Disease Cooperative Study Activities of Daily Living)

Appendix 8. C-SSRS (Columbia Suicide Severity Rating Scale)

Appendix 9. Instruction for Liposuction Procedure

Appendix 10. IP Administration Instruction for Clinical Sites

Appendix 1. Laboratory Parameters

Blood and urine samples for complete laboratory evaluation (hematology, serum chemistry, biomarker analysis and urinalysis) at Visits 1, 3, 6, 9, 12, 13 and 14 or Early Termination.

HEMATOLOGY	CHEMISTRY	URINALYSIS	BIOMARKER***
Hemoglobin	Total bilirubin	Color	Amyloid beta 40
Hematocrit	Alkaline phosphatase	Appearance	Amyloid beta 42
RBC	ALT (SGPT)	Specific gravity	Amyloid
WBC	AST (SGOT)	pH	precursor protein
MCV	Blood urea nitrogen	Protein	intracellular
MCH	(BUN)	Glucose	domain (AICD)
MCHC	Creatinine	Ketones	soluble
Neutrophils (absolute)	Glucose	Bilirubin	neuregulin-1
Lymphocytes (absolute)	Albumin	Blood	(sNRG-1)
Monocytes (absolute)	Total protein	Leukocyte esterase	
Eosinophils (absolute)	Sodium	WBC	
Basophils (absolute)	Potassium	RBC	
Platelets	Chloride	Epithelial cell	
PT-INR	Bicarbonate	Bacteria	
	Calcium	Hyaline casts	
	HCG *		
	HIV **		
	HBV**		
	HCV**		
	VDRL**		

* HCG (pregnancy test) only for all females of childbearing potential at Visits 1, 3, 12, 13 and 14 or Early Termination

** Visit 1 only

*** Visits 3 and 13, 14 or Early Termination

Appendix 2. ADAS-Cog (Alzheimer's Disease Assessment Scale-cognitive subscale)

Study	A Phase 1/2, Randomized, Double-Blind, Placebo-Controlled Study to Evaluate the Safety and Efficacy of AstroStem, Autologous Adipose Tissue Derived Mesenchymal Stem Cells, in Patients with Alzheimer's Disease						Protocol
ASP1N2 AstroStem							AST-ADP2-US01
	Date of Assessment DD-MMM-YYYY		Time of Assessment (24-hour clock)			Assessor's Initials	
Visit Number			Subject Number		Subject Initials		

Alzheimer's Disease Assessment Scale – Cognitive Behavior (ADAS-Cog)				
ADAS Initial Conversation Notes				

Instructions: For Specific instructions for all tasks, refer to the Administration Manual. The first several minutes are spent in open-ended conversation in order to assess various aspects of expressive and receptive speech. Then the remaining cognitive tests are administered. Language abilities are evaluated throughout the interview and on specific tests. Questions eliciting "yes" and "no" answers assess comprehension on a very basic level. Other questions should require specific information and well-developed communication skills.
 
Engage the subject in a short conversation about neutral topics (for example: weather, the subject's trip to the clinic, or what the subject had for breakfast). This conversation will help to put the subject at ease before the testing begins and will give the examiner an opportunity to observe how well the subject can use and understand language. There are three clinical ratings of language ability on the cognitive part of the ADAS. Use this page to record your interview notes. Documentation should be evident on this form to support rating of Spoken Language Ability, Word Finding Difficulty and Comprehension. Any rating of impairment should be supported by notes documented on this page.
				
Possible Topics	Weather	Breakfast	Clinic trip	Other
1) Comprehension				
2) Word Finding				
3) Spoken Language				
Testing Comments:	<hr/> <hr/> <hr/>			

Used with permission from the NIA Alzheimer's Disease Cooperative Study (NIA Grant AG10483)
ASP1N2 / ADAS-Cog 11Jan2017 Version

Page 1 of 23

1. Word-recall (Word List 1)

To begin testing, say: "I am going to show you some words printed on these white cards. Please read each word out loud and try to remember it, because later I will ask you to try to remember all of the words I have shown you. Ready, read the word and try to remember it."

Present each word to the subject and ask him/her to say it aloud. After all 10 words have been presented, say: "Good, now tell me all the words you can remember that were on that list." Prompt with "Any others?" as necessary. For trials 2 and 3 say: "Now I am going to show you that same list again. Read each word out loud and try to remember it." *Examiner should check a response (yes/no) for every word.*

Word recalled correctly?		
Trial 1	Yes	No
BUTTER		
ARM		
SHORE		
LETTER		
QUEEN		
CABIN		
POLE		
TICKET		
GRASS		
ENGINE		

Word recalled correctly?		
Trial 2	Yes	No
POLE		
LETTER		
BUTTER		
QUEEN		
ARM		
SHORE		
GRASS		
CABIN		
TICKET		
ENGINE		

Word recalled correctly?		
Trial 3	Yes	No
SHORE		
LETTER		
ARM		
CABIN		
POLE		
TICKET		
ENGINE		
GRASS		
BUTTER		
QUEEN		

Total Not Recalled	
Total Not Recalled	
Total Not Recalled	

If any trial not administered, please specify reason (check one):

- Not done (for reasons other than physical/cognitive impairment)
- Subject refused
- Subject unable for physical reasons
- Subject unable for cognitive reasons (if selected, enter a score of "10" in eCRF)

2. Commands

This task is designed to assess receptive speech. The subject is asked to carry out five separate commands with 1 to 5 steps per command. Each command should be read once. If the subject does not respond or looks confused, or asks for a repetition, the examiner should give the entire command one more time. Then go on to the next command. All commands should be given to every subject. *Examiner should check a response (yes/no) for every command.*

To begin testing, say: "Now I am going to ask you to do a few things. First..."

Command performed correctly?

Command	Yes	No
a. "Make a fist ." (say "Relax it" if needed upon completion).		
b. "Point to the ceiling , and then to the floor ."		
Line up a pencil, watch and card (left to right from subject's point of view) on the table.		
c. "Put the pencil on top of the card and then put it back ."		
d. "Put the watch on the other side of the pencil and turn over the card ."		
e. "Tap each shoulder twice with two fingers , keeping your eyes shut ."		

If task not administered, please specify reason (check one):

- Not done (for reasons other than physical/cognitive impairment)
- Subject refused
- Subject unable for physical reasons
- Subject unable for cognitive reasons (if selected, circle "5" on the scoring table below)

Scoring: (circle one)

0	= all commands correct
1	= 1 command incorrect
2	= 2 commands incorrect
3	= 3 commands incorrect
4	= 4 commands incorrect
5	= 5 commands incorrect

3. Constructional Praxis

This test assesses the subject's ability to copy 4 geometric forms. The forms should be presented one at a time. If the subject looks confused or dissatisfied with the drawing, or asks to try again, the subject should be allowed a second attempt for each shape. If a second attempt is made, ask the subject to indicate which one is better, and score only that attempt. *Examiner should check a response (yes/no) for every form.*

To begin testing, say: "On this piece of paper is a shape. Try to draw another one that looks just like this, somewhere on the page."

Figure drawn correctly?

[figure not shown]
Figure	Yes	No
a. Circle A closed curved figure. Small gaps do not count as errors. Size is not critical.		
b. Two overlapping rectangles Figure must be four-sided, and overlap must be similar to presented form. Changes in size are not scored.		
c. Diamond (Rhombus) Figure must be four-sided, oriented so that the points are at the top and bottom, and the sides approximately equal in length (e.g., longest side is not > 1.5 times the length of the shortest side).		
d. Cube The figure is 3-dimensional, with front face in the correct orientation, internal lines drawn correctly between corners. Opposite sides of faces should be approximately parallel.		
e. No figures drawn; scribbles; parts of forms; words instead of form		

If task not administered, please specify reason (check one):

- Not done (for reasons other than physical/cognitive impairment)
- Subject refused
- Subject unable for physical reasons
- Subject unable for cognitive reasons (if selected, circle "5" on the scoring table below)

[figure not shown]
Scoring: (circle one)

0	= all 4 drawings correct
1	= 1 form drawn incorrectly
2	= 2 forms drawn incorrectly
3	= 3 forms drawn incorrectly
4	= 4 forms drawn incorrectly
5	= no figures drawn; scribbles; parts of forms; words instead of forms

[figure not shown]
Used with permission from the NIA Alzheimer's Disease Cooperative Study (NIA Grant AG10483)
ASP1N2 / ADAS-Cog 11Jan2017 Version

Page 5 of 23

[figure not shown]
Used with permission from the NIA Alzheimer's Disease Cooperative Study (NIA Grant AG10483)
ASP1N2 / ADAS-Cog 11Jan2017 Version

Page 6 of 23

Used with permission from the NIA Alzheimer's Disease Cooperative Study (NIA Grant AG10483)
ASP1N2 / ADAS-Cog 11Jan2017 Version

Page 7 of 23

Used with permission from the NIA Alzheimer's Disease Cooperative Study (NIA Grant AG10483)
ASP1N2 / ADAS-Cog 11Jan2017 Version

Page 8 of 23

4. Naming Objects/Fingers

For this task, the subject is asked to name 12 randomly presented real objects. Objects should be presented in random order. Give the subject instructions similar to the following: "Now I am going to show you some objects. I want you to tell me what their names are. What is this called?" (present object). If the subject responds with the object's function say: "Yes, that's what it does, but what is its name?" If the subject does not respond, the examiner should give the semantic cue for that item (provided below). If the subject still does not respond or makes an error, proceed to the next object. *Examiner should check a response (yes/no) for every object/finger.*

Item	Acceptable Clue	Response correct?	
		Yes	No
Flower	grows in garden		
Bed	used for sleeping		
Whistle	makes a sound when you blow on it		
Pencil	used for writing		
Rattle	a baby's toy		
Mask	hides your face		
Scissors	cuts paper		
Comb	used on hair		
Wallet	holds your money		
Harmonica	a musical instrument		
Stethoscope	doctor uses it to listen to your heart		
Tongs	picks up food		

4. Naming Objects/Fingers (cont'd)

The subject is also asked to name the fingers on his/her dominant hand. Say: "Please place your right (or left) hand on the table. Now I am going to point to a part of your hand and I want you to tell me what it's called. What is this?" If a query is necessary say: "What is another name for this finger?"

Fingers	Response correct?	
	Yes	No
Thumb		
Index/Pointer/Forefinger		
Middle		
Ring		
Pinky/Little/Baby		

If task not administered, please specify reason (check one):

- Not done (for reasons other than physical/cognitive impairment)
- Subject refused
- Subject unable for physical reasons
- Subject unable for cognitive reasons (if selected, circle "5" on the scoring table below)

Scoring: (circle one)

0	= 0-2 items (objects and fingers) named incorrectly
1	= 3-5 items (objects and fingers) named incorrectly
2	= 6-8 items (objects and fingers) named incorrectly
3	= 9-11 items (objects and fingers) named incorrectly
4	= 12-14 items (objects and fingers) named incorrectly
5	= 15-17 items (objects and fingers) named incorrectly

5. Ideational Praxis

This task is designed to determine whether the subject can perform a familiar but complex sequence of actions. There are 5 components to this task. Place a blank long envelope, an 8 1/2 x 11" sheet of paper and a pencil in front of the subject.

Read the following instruction to the subject exactly as written:

"I want you to pretend you have written yourself a letter. Take this piece of paper, fold it so that it will fit into the envelope, and then put it into the envelope. Then seal the envelope, address the envelope to yourself, and show me where the stamp goes."

If the subject forgets part of the task, or is having difficulty, the tester should repeat the instruction for the component of the task where the subject is having difficulty. After the first complete instruction, only one additional reminder should be given for each component. *Examiner should check a response (yes/no) for every component.*

Action correct?

Component	Yes	No
a. Folds paper		
b. Put paper in envelope		
c. Seal envelope		
d. Address envelope		
e. Indicate where stamp goes		

If task not administered, please specify reason (check one):

- Not done (for reasons other than physical/cognitive impairment)
- Subject refused
- Subject unable for physical reasons
- Subject unable for cognitive reasons (if selected, circle "5" on the scoring table below)

Scoring: (circle one)

0	= all components performed correctly
1	= failure to perform 1 component
2	= failure to perform 2 components
3	= failure to perform 3 components
4	= failure to perform 4 components
5	= failure to perform 5 components

6. Orientation

This task is designed to determine how well oriented the subject is with regard to time and place. Ask the subject for each of these pieces of information one at a time. One restatement of each question is allowed (e.g. if subject confuses day and date.) Questions must not be restated based on an incorrect response but only if the subject does not understand the initial question or asks for a repetition. *Examiner should check a response (yes/no) for every question.*

Question	Response correct?
Full name: (must be exact)	
Month: (must be exact)	
Date: (± 1 day)	
Year: (must be exact)	
Day of the week: (must be exact)	
Season: (within 1 week of upcoming season or within 2 weeks of previous season)	
Place: (Partial names are acceptable, but generic terms are not) Say: "Where are we now?" or "What is the name of this place?"	
Time: (± 1 hour) Say: "Without looking at your watch, tell me approximately what time it is."	

If task not administered, please specify reason (check one):

- Not done (for reasons other than physical/cognitive impairment)
- Subject refused
- Subject unable for physical reasons
- Subject unable for cognitive reasons (if selected, circle "8" on the scoring table below)

Scoring: (circle one)

0	= all responses correct
1	= 1 response incorrect
2	= 2 responses incorrect
3	= 3 responses incorrect
4	= 4 responses incorrect
5	= 5 responses incorrect
6	= 6 responses incorrect
7	= 7 responses incorrect
8	= 8 responses incorrect

7. Word Recognition (Word List 1)

In the learning portion of this test, the subject is given one trial to learn a list of 12 words. Say: "I am going to show you some words printed on these white cards. I want you to read each word out loud and try to remember it."

In the recognition portion of this test, the examiner should say: "Now I'm going to show you another set of words. Some of the words were on the list I just showed you and others are new. For each word I want you to tell me whether it is one of the words I just showed you."

The examiner shows that first word and says either "Is this one of the words I showed you before, yes or no?", or "Did I show you this word before?" The same instruction is given before the second test word. For the remaining test words the examiner should say "How about this one?"

Check the subject's response to each word Yes or No. If the subject needs to be reminded of the task during the exam, the examiner should repeat the question and place a check in the reminder column.

***R = Reminder given**

If task not administered, please specify reason (check one):

- Not done (for reasons other than physical/cognitive impairment)
- Subject refused
- Subject unable for physical reason
- Subject unable for cognitive reasons
(Enter Max Score or "12")

Check Subject Response

Word	Yes	No	*R
NURSE			
MAGAZINE			
WIZARD			
VAN			
LEOPARD			
SALE			
SEA			
TRAIN			
COIN			
SHIP			
INSTITUTION			
MAP			
AXE			
BOARD			
CARROT			
MILK			
VOLUME			
FOREST			
ANCHOR			
GEM			
CAT			
FUND			
EDGE			
CAKE			

Total Not
Recalled
(Max Score=12)

*Reminder Given

8. Remembering Test Instructions

This item evaluates the subject's ability to remember the requirements of the Word Recognition task. The number of reminders given on the Word Recognition task are counted to rate this item. If the Word Recognition task was not completed or not attempted, then this item must not be scored.

Each instance of memory failure for the test instructions after the first two items is scored.

Scoring: (circle one)

0	None	= subject never needs extra reminders of instructions
1	Very mild	= forgets once
2	Mild	= must be reminded 2 times
3	Moderate	= must be reminded 3 or 4 times
4	Moderately severe	= must be reminded 5 or 6 times
5	Severe	= must be reminded 7 or more times

9. Comprehension

This item evaluates the subject's ability to understand speech. To rate this item consider how well the subject was able to understand the examiner's speech during the opening discussion and during the test session.
Do not count performance on Commands subtest when rating this item.

Scoring: (circle one)

0	None	= subject understands
1	Very mild	= one or two instances of misunderstanding
2	Mild	= 3-5 instances of misunderstanding
3	Moderate	= requires several repetitions and rephrasing
4	Moderately severe	= subject only occasionally responds correctly; i.e. yes/no questions
5	Severe	= subject rarely responds to questions appropriately, not due to poverty of speech

10. Word Finding Difficulty

To rate this item, the examiner must determine whether the subject has difficulty in finding the desired word in spontaneous speech during the interview and test session. Do not count performance on Naming Objects and Fingers subtest when rating this item. Documentation should be evident on page 1 to support any rating above zero.

Scoring: (circle one)

0	None	= no evidence of word finding difficulty in spontaneous speech
1	Very mild	= 1 or 2 instances, not clinically significant
2	Mild	= noticeable circumlocution or synonym substitution
3	Moderate	= loss of words without compensation on occasion
4	Moderately severe	= frequent loss of words without compensation
5	Severe	= nearly total loss of contest of words; speech sounds empty; 1-2 word utterances

11. Spoken Language Ability

This item is a global rating of the quality of speech, *i.e.*, clarity, difficulty in making oneself understood. In rating this item the examiner should consider all of the speech produced by the subject in the initial interview and the test session. Documentation should be evident on Page 1 to support any rating above zero. (Refer to the procedures manual for guidelines)

Scoring: (circle one)

0	None	= no instances where it is difficult to understand the subject
1	Very mild	= one instance of lack of understandability
2	Mild	= subject has difficulty less than 25 % of the time
3	Moderate	= subject has difficulty 25-50% of the time
4	Moderately severe	= subject has difficulty more than 50% of the time
5	Severe	= one or two word utterance; fluent, but empty speech; mute

12. Delayed Word Recall

Say to the subject, "Now I want you to try to remember the words that I showed you earlier on printed cards. Can you tell me any of those words?" Allow a maximum of two minutes for recall.

Check *each* word correctly recalled. Total equals words *not correctly* recalled.

Word recalled
correctly?

Word	Yes	No
BLOOD		
CAMP		
COTTON		
FIRE		
HALL		
LAD		
PLANT		
RIVER		
STEAM		
TOY		

Total
Not
Recalled

If any trial not administered, please specify reason (check one):

- Not done (for reasons other than physical/cognitive).
- Subject refused.
- Subject unable for physical reasons.
- Subject unable for cognitive reasons. (If selected, enter a score of "10" in eCRF)

13. Executive Function (Maze)

Present the practice maze in the correct orientation in front of the participant. Indicate where to begin and where to exit the maze. Say to the subject, "I want you to find the route from the start to the exit of this maze. Put your pencil here (point to the start) at the start. Here (point to the exit) is the exit of the maze. Try not to run into dead ends or cross solid lines. Please keep your pencil on the paper at all times." If the participant lift his or her pencil, remind him or her to keep the pencil on the page.

Once the participant has completed the Mandatory Practice Maze, proceed to the Scored Maze.

Check *each* word correctly recalled. Total equals words *not correctly* recalled.

a. Number of errors (range = 0-2)

b. Time at completion or second error
(maximum = 240 seconds total)

		
----------------------	----------------------	----------------------

If task not administered, please specify reason (check one):

- Not done (for reasons other than physical/cognitive impairment)
- Subject refused
- Subject unable for physical reasons
- Subject unable for cognitive reasons (If selected, enter a score of "5" in eCRF)

Scoring: (circle one)

0	= 0-30 seconds at completion or second error
1	= 31-60 seconds at completion or second error
2	= 61-90 seconds at completion or second error
3	= 91-120 seconds at completion or second error
4	= 121 - 239 seconds at completion or second error
5	= 240 seconds at completion or second error

14. Number Cancellation

Place the practice form face up in front of the participant. Say the following instructions word-for-word: "On the top of this page are two numbers. In this row of numbers you will find these numbers mixed in with other numbers. I'd like you to begin here" (point to the beginning of the line) and cross off each number that matches either of the two numbers at the top of the page. Please work as quickly as you can." Correct any errors and re-explain as necessary to ensure understanding of the task. Discontinue the example after 30 seconds or when the participant finishes the line, whichever is first.

Place the test form face up in front of the participant. Say the following instructions word-for-word: "On the top of this page are two numbers. Throughout this page you will find these numbers mixed in with other numbers. I'd like you to begin here" (point to the beginning of the line) and going across off each number that matches either of the two numbers at the top of the page. Please work as quickly as you can."

If the participant stops at the end of a line, before the last line, and there is still time left, ask him or her to "keep going." Discontinue the task after 45 seconds or when the participant finishes the last line, whichever is first.

a. Number of targets hit (range = 0-49)

--	--

b. Number of errors

--	--

c. Number of times reminded of task

--	--

[figure not shown]
If task not administered, please specify reason (check one):

- Not done (for reasons other than physical/cognitive impairment)
- Subject refused
- Subject unable for physical reasons
- Subject unable for cognitive reasons

Scoring: (circle one)

0	= >/= 30 total score
1	= 24-29 total score
2	= 18-23 total score
3	= 12-17 total score
4	= 6-11 total score
5	= 0-5 total score

[figure not shown]
(Example)

Used with permission from the NIA Alzheimer's Disease Cooperative Study (NIA Grant AG10483)
ASP1N2 / ADAS-Cog 11Jan2017 Version

Page 19 of 23

[figure not shown]
(Test 1)

ASP1N2 / ADAS-Cog 11Jan2017 Version
Used with permission from the NIA Alzheimer's Disease Cooperative Study (NIA Grant AG10483)

Page 20 of 23

(Test 2)

ASP1N2 / ADAS-Cog 11Jan2017 Version
Used with permission from the NIA Alzheimer's Disease Cooperative Study (NIA Grant AG10483)

Page 21 of 23

(Example)

“6” and “1”

1 2 2 4 5 9 5 6 6 6 9 1 9 6 7 8 3 2 4 3 7 2 1 4 2 2 1 2 6 6 3

Example for use with versions A, B, and C

(Test)

“2” and “8”

6	2	6	7	2	3	1	3	8	5	5	8	1	7	9	1	7	2	7	4	5	7	6	1	3	9	6	2	1	
9	4	6	9	5	7	1	8	9	5	6	5	4	2	7	1	5	2	7	9	1	7	1	1	4	2	8	5	8	
1	9	7	9	7	1	6	7	8	6	5	5	7	2	9	6	5	9	5	4	7	3	2	4	5	6	1	4	3	4
4	6	8	4	1	4	1	7	2	4	7	1	7	6	7	5	4	9	8	7	5	6	2	1	6	9	3	1	4	8
7	8	6	7	1	7	1	3	4	3	9	8	6	5	1	8	3	4	2	6	9	9	6	1	6	4	3	9	3	4
4	9	3	8	7	2	5	4	4	8	7	6	4	1	4	7	2	6	8	7	5	6	3	2	6	4	4	6	8	4
4	8	3	4	7	5	4	4	7	9	7	3	6	8	6	5	4	7	4	3	4	9	2	5	3	5	4	7	3	5
4	9	3	3	8	1	8	4	2	6	5	6	6	1	7	2	4	2	9	7	9	7	6	1	5	1	4	1	9	8

14

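### The ADAS-Cog form scores delayed recall (item 12) against ten words that appear in neither word list on the form, so as printed the item cannot register recall

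*Protocol*

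**What the plan says.** Protocol 6.1.4 and SAP 4.7.1 make the change in ADAS-Cog score from baseline (Visit 3) to Week 30 the primary efficacy variable. Protocol 4.2.1 and 4.3.1 send the site to Appendix 2 for the form at both visits. Protocol 3.6.2 also schedules it at Visits 6, 9, 12 and 14 and at early termination.

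Three items of that form use word lists:

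- Item 1 is headed "1. Word-recall (Word List 1"). It presents ten words on cards. Before trials 2 and 3 the examiner says "Now I am going to show you that same list again".
- Item 7 is headed "7. Word Recognition (Word List 1"). Twelve words are learned and then tested among 24 printed words.
- Item 12, delayed recall, carries no list label. The prompt is "Now I want you to try to remember the words that I showed you earlier on printed cards". The rater ticks each of ten printed words as recalled or not, and the score is the number not recalled.

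On the total, neither Protocol 6.1.4 nor SAP 4.7.1 says which of the 14 items are summed or names a scoring source. Item 1 has a separate total for each of three trials. Item 14 records "Number of targets hit (range = 0-49"), a count of errors, and "Number of times reminded of task", and then assigns bands such as "24-29 total score". The form refers raters to an Administration Manual for instructions on every task.

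**The concern.** A delayed-recall item works only if it is scored on the words the subject was shown. Here the prompt points back to the cards, but the tick boxes hold a different set of words. A rater who follows the page records a complete failure for a subject who remembers everything. A rater who notices the mismatch has to improvise, and nothing in the Protocol or SAP ensures that every rater improvises alike, or does so at every visit.

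Two things are at stake, and they differ in kind. If everyone scores the page literally, the primary scale loses one item. If some forms are scored literally and others on the item 1 words, and the two methods fall on different visits of the same subject, the change score picks up an artefact unrelated to cognition. With 11 subjects per arm, a few such subjects would be visible in an arm mean.

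**Working it through.** The plan states no ADAS-Cog range, SD or target difference, so there is no figure to reproduce. The check is a comparison of lists followed by simple arithmetic.

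**Step 1: the lists in Appendix 2.**

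- Item 1 (the same ten words in all three trials, in different order): BUTTER, ARM, SHORE, LETTER, QUEEN, CABIN, POLE, TICKET, GRASS, ENGINE.
- Item 7 (24 test words): NURSE, MAGAZINE, WIZARD, VAN, LEOPARD, SALE, SEA, TRAIN, COIN, SHIP, INSTITUTION, MAP, AXE, BOARD, CARROT, MILK, VOLUME, FOREST, ANCHOR, GEM, CAT, FUND, EDGE, CAKE.
- Item 12 (ten scoring words): BLOOD, CAMP, COTTON, FIRE, HALL, LAD, PLANT, RIVER, STEAM, TOY.

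Overlap of item 12 with item 1: 0 of 10. Overlap of item 12 with item 7: 0 of 10.

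**Step 2: the score as printed.** Item 12 score = 10 − (number of the printed item 12 words recalled).

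- All ten item 1 words recalled: 10 − 0 = 10.
- Nothing recalled: 10 − 0 = 10.
- Unable for cognitive reasons: 10, as the form instructs.

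Apart from chance guesses, every subject scores 10 at every visit. The item's contribution to the change is 10 − 10 = 0 in both arms.

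**Step 3: the list differs between two visits of one subject.** Suppose the subject truly recalls k of the item 1 words at both visits, so the true change is 0.

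- Baseline on the printed list, Week 30 on the item 1 words: (10 − k) − 10 = −k, recorded as an improvement of k points.
- The reverse order: 10 − (10 − k) = +k, recorded as a decline of k points.

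**Step 4: effect on an arm mean.** Protocol 6.2 and SAP 3.2 plan 11 subjects per arm (SAP 3.2 says about 11). If all 11 contribute, one affected subject moves the arm mean by k/11. That is 1/11 = 0.09 points per word, and at most 10/11 = 0.91 points for one subject with k = 10. The between-arm difference moves by the same amount unless the other arm has offsetting cases.

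**Step 5: which list was meant.** Item 12 has ten scoring words. Item 1 presents ten and item 7 teaches twelve, so item 12 appears to be built for the item 1 list. This supports scoring it on whatever item 1 presents. It does not show which printed page is wrong, because the cards themselves are not reproduced.

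**The case against.** The strongest reply is that the form is not the whole procedure. It cites an Administration Manual that is not among the documents, and trained raters may have scored the words actually on the cards. The cards might even carry BLOOD, CAMP and the rest, in which case the printed item 1 list is the faulty one. The harm in steps 3 and 4 also needs a change of list between visits, which no document reports.

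Most of this stands, and it limits the point. The mismatch is proved only for the form as printed, and the documents do not establish its cause or which list is at fault. It does not remove the contradiction: a rater following a manual would still face tick boxes for words that differ from those printed for presentation.

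Two stronger readings are tempting. A reader might infer that the primary comparison is biased. The documents do not support that. Consistent literal scoring adds about 0 in both arms, and if raters stay blinded there is no reason for the choice of list to follow treatment. Inconsistent scoring would mainly add noise, although chance imbalance matters with arms of 11.

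A reader might also infer that the primary total has no derivation at all and will be settled after results are seen. That goes too far. The manual may supply the rules for items 1 and 14, and a figure directly after the item 14 count boxes is not reproduced in the text I worked from. The interim look in SAP 4.9 covered vital signs, concomitant medications and adverse events, not ADAS-Cog. A rule fixed before unblinding would not bias the comparison. What remains is that neither Protocol 6.1.4 nor SAP 4.7.1 names the items or adopts a scoring source.

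**Conclusion.** The inconsistency is real and concerns the instrument for the primary efficacy variable. As printed, item 12 cannot tell perfect delayed recall from none and contributes about 0 to the change score. That is a lost item, not a distortion between arms. If a subject's baseline and Week 30 were scored on different lists, the artefact would be one point per recalled word, or 0.09 points per word on an arm mean. This assumes 11 contributing subjects per arm and unchanged true recall. With no SD or target difference stated, it cannot be expressed as a loss of power.

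How raters actually scored is unknown, and completed forms may already exist. SAP 4.9 reports that the first four subjects had completed Visit 4, so their Visit 3 baselines were due, although SAP Section 1 says Version 1 was approved before the first patient visit.

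This should be fixed before unblinding. The unspecified composition of the total is a secondary point and calls only for clarification.

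**What to change.** Before unblinding:

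- **Reconcile the lists.** Compare the item 1 and item 12 lists with the cards actually shown. Score item 12 on the ten words presented in item 1 at that visit, and print the list label on item 12.
- **Score one way throughout.** Apply the same item 12 scoring at all ADAS-Cog visits, and re-score completed forms wherever the spoken words are in source.
- **If any baseline cannot be re-scored,** leave item 12 out of the primary total for all subjects, or pre-specify an analysis without item 12 for everyone. Keeping uncorrected scores for some subjects and corrected scores for others would mix two effective scales in an arm mean. Report the number of affected subjects by arm.
- **Clarify the total in the same edit.** State in SAP 4.7.1 which items form the ADAS-Cog total and which source governs scoring, including how the three item 1 trials and the item 14 counts are combined.

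The cost is a corrected form, a memo to raters, a short addition to the SAP, some re-scoring, and possibly the instrument owner's permission. Item 12 provides tick boxes only for the printed words, so some baselines may not be recoverable. No extra visits or subjects are needed.
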